4.3 Subject Recruitment and Screening

Subject recruitment is performed by the patient's treating physician in clinical practice during consultation at a Penn Medicine location. All eligible candidates are invited to participate in the research in the following manner:

1. During the patient's initial surgical consultation, the treating physician or a member of the study team describes the study and its risks and benefits.
2. The potential subject is given a copy of the consent form to review and have all questions answered by the PI or Sub-I. If the patient decides to participate, the consent form is signed.
3. The subject is screened for history of iodine/shellfish allergy by clinical staff.
4. The subject is scheduled for injection at a Penn Medicine location and advised to call with any questions.

4.4 Duration of Study Participation

Each subject participates in the treatment phase of the trial for approximately 2-4 weeks until surgical resection then is followed for 5 years for survival and recurrence.

4.5 Total Number of Subjects and Sites

It is expected that up to 500 subjects will be enrolled in this study, see [Section 7.3](#) for the sample size determination.

4.6 Vulnerable Populations

Pregnant women, prisoners, children, or other vulnerable populations will not be included. Although not directly targeted, mentally disabled persons, economically or educationally disadvantaged persons, and/or employees or students of the University of Pennsylvania will not be denied enrollment and any special protections and/or additional safeguards will be undertaken in order to protect the rights and welfare of these subjects from coercion or undue influence as appropriate. Students or employees of Penn are informed that their decision to participate does not affect their standing with the University in any way.

4.7 Evaluable Subjects

4.7.1 Non-Evaluable: When and How to Withdraw Subjects

Subjects will be not evaluable if study visits 2 and 3 are not complete. Reasons may include:

1. The subject decides that he/she does not wish to have their surgery.

CONFIDENTIAL

This material is the property of the University of Pennsylvania.

2. The subject experiences a SAE or an AE during the injection, which would require an intervention of steroids or epinephrine.
3. The subject fails to meet eligibility criteria.
4. The PI or sub-I determine it is in the subject's best interest to not continue in the study.
5. Other reasons such as logistical or scheduling conflicts.

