1.7.3 Assessment of Potential Risks and Benefits

The PI weighs the risks of participating in the study with the potential benefits of participating in the study for each subject enrolled. We feel that the very low risk of adverse reactions expected from the study compared to the practical potential benefit of improving nervous system tumor resection and related outcomes using a non-toxic imaging agent are acceptable.

2 Study Objectives

The primary study objective is to determine safety/efficacy of high dose, delayed indocyanine green (second window ICG) during surgery of nervous system tumors.

The first objective is to determine diagnostic test characteristics (sensitivity/specificity) of delayed, high dose indocyanine green (second window ICG) as a diagnostic aid during surgery of nervous system tumors. Additionally, to optimize timing and dose of second window IcG during surgery of nervous system tumors, based on sensitivity/specificity. Lastly, to compare SOC dyes with indocyanine green to determine efficacy for tumor visualization, answering the question is one dye superior to another, more accurate and precise.

3 Study Design

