4.7.2 Data Collection

Subject study data is entered into Penn CTMS and a RedCap database as part of the Center of Precision Surgery in order to capture demographic and study data as well as surgeon impression from surgery, which are both encrypted and password protected databases maintained on secure servers.

Data collection and access to medical records will continue for all evaluable subjects on survival and recurrence data for up to five years after their surgery.

5 Study Intervention

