5.1.2 Treatment Regimen

The dose is a single infusion of up to 5 mg/kg reconstituted indocyanine green injected intravenously in the dark, within 72 hours of the operation. Alternately, subjects may receive a 25 mg dose of indocyanine green administered by the anesthesiology team during induction. If subjects experience any AEs, please reference [Section 8.2](#) for protocol intervention. There is no second dose.

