5.8 Receiving, Storage, Dispensing and Return

Penn Investigational Drug Service (HUP and PPMC) or PAH Pharmacy is responsible for all aspects of receiving, storage, dispensing and return of the study intervention.

6 Study Procedures

When the infusion is done pre-operatively (Table 2a), study participation consists of 1) a screening visit, followed by 2) an infusion visit 72 hours prior to surgery, and 3) the operative visit.

Table 2a Pre-Op Infusion Schedule of Evaluations

Study Procedure	Visit 1: Screening	Visit 2: Infusion Visit	Visit 3 Operative Visit	Annual Assessment (Until Year 5)
Informed Consent	X			
Review Inclusion/Exclusion Criteria	X			

CONFIDENTIAL

Study Procedure	Visit 1: Screening	Visit 2: Infusion Visit	Visit 3 Operative Visit	Annual Assessment (Until Year 5)
Demographics/Medical History	X			
Physical Examination	X			
Vital Signs: BP, HR, RR	X	X	X	
Height and Weight	X			
Pregnancy Test	X			
Prior/Concomitant Medications	X			
Iodine/Shellfish Allergy Test	X			
Dispense IP		X		
AE/Unanticipated Problems		X	X	
Annual Medical Record Review: Survival, Recurrence				X

AE = adverse event; BP = blood pressure; HR = heart rate; IP = investigational product; RR = respiratory rate

When the infusion is done intraoperatively (Table 2b), study participation consists of 1) a screening visit, followed by 2) the operative visit in which the anesthesiology team may infuse the NIR drug intra-operatively. This will be a 25mg infusion.

Table 2b Intra-op Infusion Schedule of Evaluations

Study Procedure	Visit 1: Screening	Visit 2: Operative Visit	Annual Assessment (Until Year 5)
Informed Consent	X		
Review Inclusion/Exclusion Criteria	X		
Demographics/Medical History	X		
Physical Examination	X		
Vital Signs: BP, HR, RR	X	X	
Height and Weight	X		
Pregnancy Test	X		
Prior/Concomitant Medications	X		
Iodine/Shellfish Allergy Test	X		
Dispense IP to Anesthesia for injection intra-op		X	
AE/Unanticipated Problems		X	
Annual Medical Record Review: Survival, Recurrence			X

AE = adverse event; BP = blood pressure; HR = heart rate; IP = investigational product; RR = respiratory rate

CONFIDENTIAL

This material is the property of the University of Pennsylvania.

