6.3 Visit 3: Operative Visit

Patients will come to one of the University of Pennsylvania Health System hospitals to undergo removal of their tumor as clinically indicated. Surgical approach and exposure are performed according to standard of care. The entire procedure is photo-documented and recorded as per standard of care. There are five phases of NIR imaging; however, one or more of the phases may be omitted. Patients receiving intra-op ICG by anesthesia will report day of surgery and not have an infusion suite visit.

CONFIDENTIAL

This material is the property of the University of Pennsylvania.

Dura View: upon opening the skull at the level of the dura but prior to opening the dura, a brief view of the dura is obtained with the NIR imaging system – Dura View.

Cortex View: upon opening the dura but prior to violating the cortex of the brain, another brief view of the cortex is with the NIR imaging system – Cortex View.

Tumor View: Prior to initial resection but upon identification of the tumor, the NIR imaging system (i.e. VS₃ Iridium, Stryker 1588 AIM) is used to visualize the tumor in its native and untouched form. The lights in the OR are turned off and the infrared imaging system is turned on. The video screen displays the images of the tumor area, and the surgeon measures the spectral reading from the tumor. The imaging system captures the infrared signal that is emitted from the indocyanine green that has been taken up by the tumors. Initial tumor fluorescence will be recorded and visualized. After initial visualization, surgical resection will proceed as per standard of care. A NIR microscope (i.e. Leica FL800, Zeiss INFRARED™ 800) will be used to assist with the surgical resection.

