6.4 Annual Assessments and Subject Follow-Up

For a period of up to 5 years after enrollment, the PI and research team will review the subjects' medical records annually to obtain information about their medical condition. Re-occurrence will be tracked with the subject's oncologist. We utilize the standard protocol used by the oncologist for tracking re-occurrence, which includes, but is not limited to MRI, CT, or PET scans.

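### The evaluability rule in 4.7.1 cannot be met on the 25 mg induction schedule, and 3.2 and 7.1 disagree on whether the primary estimate is limited to second window ICG

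*Combined protocol and SAP*

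**What the plan says.** The protocol allows two schedules for giving ICG. One is a weight-based infusion in the 72 hours before the operation (Table 2a). The other is in Section 5.1.2: "subjects may receive a 25 mg dose of indocyanine green administered by the anesthesiology team during induction".

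On evaluability, Section 4.7.1 says: "Subjects will be not evaluable if study visits 2 and 3 are not complete". It then lists five possible reasons: surgery declined, a reaction during injection, ineligibility, an investigator decision, and logistics.

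For the induction schedule, Section 6 (text introducing Table 2b) says that "study participation consists of 1) a screening visit, followed by 2) the operative visit". Section 6.3, whose heading makes the operation Visit 3, says: "Patients receiving intra-op ICG by anesthesia will report day of surgery and not have an infusion suite visit".

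On the primary endpoint, Section 3.2 names the test characteristics of second window ICG against histopathology. Section 2 gives that term its meaning, "high dose, delayed indocyanine green (second window ICG", with the bracket closing there. Section 7.1 restates the endpoint as the accuracy of ICG fluorescence against H&E. It does not repeat the second window limit, separate the regimens or name an analysis set.

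**The concern.** There are two separate faults, and they pull in opposite directions.

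First, the only definition of an evaluable subject is written in the visit numbers of one schedule. Applied literally, it makes every subject on the other permitted schedule non-evaluable, including those who received ICG, had the operation and supplied specimens.

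Second, Section 7.1 as written does not keep those same subjects out of an estimate that Section 3.2 reserves for second window ICG. Two analysts could each follow the document and report different populations: one drops induction subjects under 4.7.1 or 3.2, and the other includes them under 7.1.

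The stake is what the reported sensitivity and specificity describe. The analyses are descriptive (Section 7.4), but Section 7.3 intends the study to feed the planning of a later randomized trial. That use requires knowing which regimen the figures belong to.

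**Working it through.** No power or sample size figure bears on this; Section 7.3 says there is no calculation behind the 500. The check sets the texts side by side and does a small count.

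**Step 1: visit logic.** Section 4.7.1 needs both Visit 2 and Visit 3.

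| | Pre-operative infusion (Table 2a) | Induction (Table 2b) | Induction (numbering of 6.2 and 6.3) |
|---|---|---|---|
| Visit 2 | infusion | operation | infusion visit, does not occur |
| Visit 3 | operation | none | operation |
| Can 4.7.1 be met? | yes | no | no |

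Under either numbering one required visit is missing, so no induction subject can satisfy the rule.

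**Step 2: was that intended?** The five reasons in 4.7.1 describe people who did not get through infusion and surgery. Section 1.5 uses the term similarly: its 26 non-evaluable subjects (4 + 4 + 9 + 5 + 4 = 26 by reason) are listed apart from the 296 infused. Neither place suggests that a subject who received ICG at induction and was operated on should be left out. The likely explanation is that 4.7.1 was not updated for Table 2b.

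**Step 3: primary endpoint.**

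- Section 3.2: second window ICG. Section 2: high dose and delayed.
- Section 7.1: ICG fluorescence, with no limit.
- Induction dose: 25 mg flat, not delayed. Body weight is not given. At an assumed 70 kg, 25 / 70 = 0.36 mg/kg; over 50 to 100 kg the range is 25 / 50 = 0.50 to 25 / 100 = 0.25 mg/kg. The weight-based doses given so far are 2.5 and 5 mg/kg.

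The induction schedule therefore does not fit the description in Section 2. Read alone, 3.2 leaves induction subjects out of the primary estimate; 7.1 does not.

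**Step 4: what pooling would do.** Let w be the share of pathology-positive specimens that come from induction subjects. Then

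pooled sensitivity = (1 − w) × second window sensitivity + w × induction sensitivity,

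which differs from second window sensitivity by w × (induction − second window). Specificity behaves the same way, with w taken over pathology-negative specimens. The documents give neither w nor accuracy by regimen, so size and sign cannot be computed. The choice of regimen is left to the neurosurgeon (Section 3.1) or the PI (Study Summary), without randomization (Section 5.3). A pooled figure would therefore also depend on which patients were chosen for induction.

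**Step 5: who is affected.** By January 2019, 110 subjects had received 2.5 mg/kg and 186 had received 5 mg/kg: 110 + 186 = 296, which is every infused subject. None had 25 mg, so the problem concerns enrolment after that date.

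**The case against.** The best reply on 4.7.1 is that it is a numbering slip with recoverable intent. Section 6.2 applies the infusion visit only to subjects dosed within 72 hours of surgery, and a sensible reader would not exclude induction subjects. That is probably right about intent, but the written rule still gives the wrong answer for a permitted schedule. Reading the rule as excluding only subjects with neither visit complete does not rescue it: an infused subject who never had the operation would then be evaluable, with no specimen to analyse.

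On the endpoint, the reply is that 3.2 is current text, that the Study Summary and Section 2 repeat the term second window, and that 7.1 merely expands 3.2. The plan to optimise dose and timing using sensitivity and specificity (Part IIb) also implies accuracy by regimen. This has force. It rules out saying that the protocol chooses to pool; the two sections are simply inconsistent. It does not remove the gap, because 7.1 is the analysis text and Part IIb itself speaks only of second window ICG.

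Three stronger readings are tempting, and the documents do not support them.

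- **Pooling is required.** Section 6.3 has every subject and specimen count in the final analysis, but in context this concerns an unexpected diagnosis at surgery. It does not call for one estimate across regimens.
- **Section 7.1 authorises pooling.** It is only silent, and 3.2 points the other way.
- **The induction share can be capped from the 500 and the interim counts.** The documents do not settle whether the 500 counts consented or infused subjects. The 185 per dose in Section 7.2 is an approximate trigger for an interim look, not a quota.

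**Conclusion.** Both faults stand. As written, 4.7.1 makes every induction subject non-evaluable, apparently by oversight. Sections 3.2 and 7.1 disagree on whether the primary accuracy estimate is limited to second window ICG, and no passage says whether evaluable status defines that analysis set.

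The effect on the results cannot be sized. No induction subject was among the 296 infused by January 2019, and the documents give no later induction count, no accuracy by regimen and no specimen shares. The conclusion rests on the natural reading of 4.7.1 (both visits needed) and on Section 2's description of second window ICG. It does not depend on the assumed body weights, which only illustrate the dose contrast. This should be put right before the accuracy analysis is run; it does not undermine the design.

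**What to change.** 1. **Section 4.7.1.** Define evaluability by pathway and by events: ICG given and operation done. For the accuracy analysis, also require an imaging call with matching histopathology, because Section 6.3 lets imaging phases be omitted and a completed operation does not guarantee usable data.
2. **Table 2b and Section 6.3.** Give the operative visit of induction subjects one consistent number.
3. **Analysis set.** Say whether evaluable status defines the set used in 7.1.
4. **Section 7.1.** State that the primary estimate uses second window subjects, as in 3.2. The sponsor should state which of its existing regimens that term covers, since the infusion is described only by upper limits (5 mg/kg, 72 hours). Report induction subjects as a separate descriptive stratum.

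The cost is wording in these places and one extra stratum from data already collected. The downside is fewer specimens in the primary estimate than under full pooling, by a number the documents do not allow one to calculate. No dose, timing or clinical rule is changed.

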4.7.2 Data Collection

Subject study data is entered into Penn CTMS and a RedCap database as part of the Center of Precision Surgery in order to capture demographic and study data as well as surgeon impression from surgery, which are both encrypted and password protected databases maintained on secure servers.

Data collection and access to medical records will continue for all evaluable subjects on survival and recurrence data for up to five years after their surgery.

5 Study Intervention

5.1 Investigational Product

5.1.1 Description

Indocyanine green is a NIR contrast agent. It is a water-soluble tricarbocyanine dye supplied as a lyophilized powder in 25 mg vials. The powder will be reconstituted in sterile diluent.

5.1.2 Treatment Regimen

The dose is a single infusion of up to 5 mg/kg reconstituted indocyanine green injected intravenously in the dark, within 72 hours of the operation. Alternately, subjects may receive a 25 mg dose of indocyanine green administered by the anesthesiology team during induction. If subjects experience any AEs, please reference [Section 8.2](#) for protocol intervention. There is no second dose.

5.2 Approved Product

5.2.1 Description

Gleolan (aminolevulinic acid hydrochloride) is an optical imaging agent for oral solution. The 50-mL, clear vial contains 1,500 mg of lyophilized ALA HCl powder (equivalent to 1,170 mg ALA). After reconstitution, the product has a concentration of 30 mg ALA HCl per mL (equivalent to 23.4 mg ALA per mL).

5.2.2 Treatment Regimen

The recommended reconstituted oral dose of Gleolan is 20 mg/k administered 3 hours (range 2 to 4 hours) before anesthesia. If subjects experience any AEs, please reference [Section 8.2](#) for protocol intervention. There is no second dose.

CONFIDENTIAL

This material is the property of the University of Pennsylvania.

5.3 Method for Assigning Subjects to Treatment Groups

As this is an open-label study, there will be no randomization of treatment.

5.4 Preparation and Administration of Study Drug

Penn Investigational Drug Service (HUP and Penn Presbyterian Medical Center [PPMC]) or Pennsylvania Hospital (PAH) Pharmacy prepares the study intervention upon notification. The study intervention is administered after preparation once a member of the study team picks up the drug(s) and delivers to the HUP CTRC or the in-house INCU RN, Farm Journal Building at PAH or the in-house ICU RN, or the Abramson Cancer Center (ACC) at PPMC in a light sensitive bag(s), where the staff nurse administers the drug.

5.5 Prior and Concomitant Therapy

Any therapies that are normally not exclusionary criteria for surgical resection are permitted in this study.

5.6 Packaging

Indocyanine green is supplied in a kit (NDC 17238-424) containing six 25mg indocyanine green vials and six 10mL sterile water plastic vials. The label is provided in [Section 15](#).

Gleolan is supplied as 1,500 mg of lyophilized ALA HCl powder (equivalent to 1,170 mg ALA), for oral solution in a 50-mL clear, colorless, glass vial with a rubber stopper and an aluminum crimp seal.

5.7 Blinding of Study Drug

As this is strictly an open-label imaging study, no blinding of the drug is necessary.

5.8 Receiving, Storage, Dispensing and Return

Penn Investigational Drug Service (HUP and PPMC) or PAH Pharmacy is responsible for all aspects of receiving, storage, dispensing and return of the study intervention.

6 Study Procedures

When the infusion is done pre-operatively (Table 2a), study participation consists of 1) a screening visit, followed by 2) an infusion visit 72 hours prior to surgery, and 3) the operative visit.

Table 2a Pre-Op Infusion Schedule of Evaluations

Study Procedure	Visit 1: Screening	Visit 2: Infusion Visit	Visit 3 Operative Visit	Annual Assessment (Until Year 5)
Informed Consent	X			
Review Inclusion/Exclusion Criteria	X			

CONFIDENTIAL

Study Procedure	Visit 1: Screening	Visit 2: Infusion Visit	Visit 3 Operative Visit	Annual Assessment (Until Year 5)
Demographics/Medical History	X			
Physical Examination	X			
Vital Signs: BP, HR, RR	X	X	X	
Height and Weight	X			
Pregnancy Test	X			
Prior/Concomitant Medications	X			
Iodine/Shellfish Allergy Test	X			
Dispense IP		X		
AE/Unanticipated Problems		X	X	
Annual Medical Record Review: Survival, Recurrence				X

AE = adverse event; BP = blood pressure; HR = heart rate; IP = investigational product; RR = respiratory rate

When the infusion is done intraoperatively (Table 2b), study participation consists of 1) a screening visit, followed by 2) the operative visit in which the anesthesiology team may infuse the NIR drug intra-operatively. This will be a 25mg infusion.

Table 2b Intra-op Infusion Schedule of Evaluations

Study Procedure	Visit 1: Screening	Visit 2: Operative Visit	Annual Assessment (Until Year 5)
Informed Consent	X		
Review Inclusion/Exclusion Criteria	X		
Demographics/Medical History	X		
Physical Examination	X		
Vital Signs: BP, HR, RR	X	X	
Height and Weight	X		
Pregnancy Test	X		
Prior/Concomitant Medications	X		
Iodine/Shellfish Allergy Test	X		
Dispense IP to Anesthesia for injection intra-op		X	
AE/Unanticipated Problems		X	
Annual Medical Record Review: Survival, Recurrence			X

AE = adverse event; BP = blood pressure; HR = heart rate; IP = investigational product; RR = respiratory rate

CONFIDENTIAL

This material is the property of the University of Pennsylvania.

6.1 Visit 1: Initial Consult (approximately 2 weeks prior to operation)

Patients are given the consent form to examine at their leisure and are encouraged to ask questions and have time to have all questions answered. The PI or member of the study team obtains consent from the patient. He/she will be screened for history of iodine/shellfish allergy by clinical staff.

6.2 Visit 2 (CTRC, Infusion visit within 72 hours before operation)

For subjects receiving ICG with 72 hours of surgery, they will arrive at the Perelman Center for Advanced Medicine Clinical & Translational Research Center, [name] or the ACC, Farm Journal Building at PAH, [name], or the ACC at PPMC, [name] for their infusions at their respective infusion locations within 72 hours prior to the scheduled surgery to receive their injection of indocyanine green by trained nursing staff. The nursing staff places a peripheral IV and calls the pharmacy for the scheduled infusion of up to 5 mg/kg of indocyanine green diluted in sterile water administered intravenously in the dark, over 40 minutes. The nurse monitors subjects pre infusion, during the 40-minute infusion and for 30 minutes post infusion for any signs of anaphylaxis. For all AEs and prescribed treatment, please see **Section 6.5** and **8.2** Expected Adverse Events and Treatment).

During the study visit, subjects' vital signs are monitored as follows: pre infusion; then at 5 minutes after infusion starts, then at every 15 minutes over the 40-60 minute infusion time frame. During the post infusion 30 minute observation period, vital signs are completed at 10-minute intervals and the subject is monitored for any signs of anaphylaxis. The following vital signs are monitored and recorded during each time point: HR, BP, skin color, and oxygen levels (pulse oximetry) and the subject is observed for any adverse sign or symptoms that could include but is not limited to HTN, mild pain or discomfort at infusion site and signs of anaphylaxis. Symptoms are treated according to prescribed interventions outlined in the ICG Treatment Plan.

The Neurosurgeon may want to compare both indocyanine green with other Standard of Care NIR dyes (ex: 5-ALA) intra-operatively to see which dye localizes more accurately and precisely at the region of interest. This may result in using more than one dye for your surgery.

